14.1. Compliance with Regulations Applicable to Clinical Trials

The study will be conducted according to the laws, regulations and administrative provisions relating to the implementation of Good Clinical Practice in the conduct of clinical trials.

14.2. Informed Consent

The principles of Informed Consent, according to the Declaration of Helsinki 1964 and all its updates, will be followed. A subject should not enter a clinical study until he/she has been properly informed, has been given time to contemplate participation, and has freely given his/her consent by signing and dating the IRB-approved informed consent form. This must be done prior to performing any study-related procedures.

The proposed consent form and any other documents relevant to the consent process must be submitted to the Institutional Review Board (IRB), together with the protocol, and must be approved prior to the study start.

A copy of the fully signed and dated Informed Consent and any other documents relevant to the consent process will be given to the subject and the original will be maintained at the site.

14.3. Institutional Review Board (IRB)

The study must have approval, in writing, by an appropriate Institutional Review Board (IRB).

Records of the IRB review and approval of all documents pertaining to this study must be kept on file by the investigator.

Serious or unanticipated adverse events (SAEs) must also be reported to the IRB by the Investigator.

14.4. Protocol Amendments

Protocol amendments must be approved by the IRB prior to implementation.

14.5. Subject Confidentiality

All subject data will be identified only by a subject identification number and date of birth.

15. Guide for participants

Phase I - Self-Administered Questionnaire

I.D.: _____ DATE: _____

Please read the cover and the back cover of the device and answer the following questions:

1. Is the device for Dry Mouth Relief?

- Yes
- No

2. Does the device fit your needs?

- Yes
- No

3. If the device fits your needs, please check a box (only one):

- I can use the device.**
- I cannot use the device because, either:**
 - I'm under 18 years of age.
 - I suffer from epileptic disorder.
 - I'm allergic to gold or silicone rubber.
- I need a professional consultation before buying the device because, either:**
 - I use a pacemaker.
 - I'm pregnant.
 - I suffer from a psychiatric or psychological disorder.
 - I suffer from an involuntary movement disorder (for example Parkinson's disease).
 - I have a neurologic disorder in the head and neck area (for example trigeminal neuralgia).

Phase II - Interviewer-administered questionnaire

I.D.: _____ DATE: _____

Please read the user manual and hold the device.

Firstly, your oral cavity will be examined.

Next, you will be asked the following questions and to perform the following tasks:

- 1. How many times can you use the device in a day and how many minutes (maximum time) you can use the device in one session? (See page 2)**
- 2. How do you turn ON and OFF the device? (See page 6)**
- 3. How do you insert the device in your mouth? (See pages 7, 8 and 9 and watch the video “How to use the SaliPen device to stop dry mouth”)**
- 4. How do you take the device out of your mouth? (See pages 7, 8 and 9)**
- 5. How do you detach and reattach the white extraoral command unit from the blue intraoral stimulating unit? (See page 6)**
- 6. Did you experience discomfort with the SaliPen in your mouth?**
- 7. Did you experience difficulties in using the SaliPen?**

Finally, your oral cavity will be examined again.

16. Evaluation Sheets

Phase I

Subject I.D.: _____

EVALUATOR NAME: _____

Date: _____

Step 1: Anamnesis taken by the evaluator

Ruling	Parameters	yes	no
Indication	Xerostomia		
Contraindications	Under 18 years old		
	Epileptic disorder		
	Allergy to gold		
	Allergy to silicone		
Precautions – medical advice recommended before purchase	Pacemaker		
	Pregnant		
	Psychiatric or psychological disorder		
	Involuntary movement disorder (e.g., Parkinson's disease)		
	Neurologic disorder in the head and neck area (e.g., trigeminal neuralgia)		

Step 2: Self-Administered Questionnaire - Subject pre-purchase selection of the study product

Subjects will be asked to read the cover and the back cover of the device package and answer the following questions:

Question / Statement	Participant's answer	Correct answer	Success (1) / Failure (0)
1. Is the device for Dry Mouth Relief?	 Yes  No	 Yes  No	
2. Does the device fit your needs?	 Yes  No	 Yes  No	
3. If the device fits your needs, please check a box (only one):			
I can use the device	 Yes  No	 Yes  No	

Question / Statement	Participant's answer	Correct answer	Success (1) / Failure (0)
I cannot use the device because, either: 
 • I'm under 18 years of age. • I suffer from epileptic disorder. • I'm allergic to gold or silicone rubber. 	 Yes  No	 Yes  No	
I need professional advice before using the device because, either: 
 • I use a pacemaker. • I'm pregnant. • I suffer from a psychiatric or psychological disorder. • I suffer from an involuntary movement disorder (for example Parkinson's disease). • I have a neurologic disorder in the head and neck area (for example trigeminal neuralgia). 	 Yes  No	 Yes  No	

Step 3: Summary evaluation (to be completed by the evaluator)

Total questions/statements for those with dry mouth: 5

Number of correct answers: _____

Total questions/statements for those without dry mouth: 2

Number of correct answers: _____

Passed? (all answers/statements should be correct):

Yes
 No

Phase II

Subject I.D.: _____

Step 1: Oral soft tissue examination

EVALUATOR NAME: _____

DATE: _____

	Normal	Abnormal	If Abnormal, please specify findings
Labial Mucosa (including lips)			_____
Buccal Mucosa			_____
Mucogingival Folds			_____
Gingival Mucosa			_____
Edentulous Ridge/Retromolar area			_____
Tongue			_____
Sublingual Area/floor of mouth			_____
Submandibular area			_____

Step 2: Assessment of subject performance
EVALUATOR NAME: _____

DATE: _____

Please evaluate how the participant addresses the following questions/tasks:

Questions	Participant's answer	Correct answer	Success (1) / Failure (0)
1. How many times in a day and how many minutes (maximum time) you can use the device in one session?			
Tasks	Evaluation		Success (1) / Failure (0)
2. How do you turn on ON and OFF the device?			
3. How do you insert the device in your mouth?			
4. How do you take the device out of your mouth?			
5. How do you detach and reattach the white extraoral command unit from the blue intraoral stimulating unit?			
Subject assessment (place an x where relevant for you) Note: Success (1) is meant if options 2 or 3 were chosen Failure (0) is meant if option 1 was chosen			Success (1) / Failure (0)
6. Did you experience discomfort with the SaliPen in your mouth?	1- Severe discomfort 2- Moderate discomfort 3- No discomfort		
7. Did you experience difficulties in using the SaliPen?	1- Severe discomfort 2- Moderate discomfort 3- No discomfort		

Summary evaluation:
Total questions/tasks/self-assessments: 7

Number of points: _____

Passed? (minimum 6 points):

Yes
 No

Step 3: Oral soft tissue examination

EVALUATOR NAME: _____

DATE: _____

	Normal	Abnormal	If Abnormal, please specify findings
Labial Mucosa (including lips)			
Buccal Mucosa			
Mucogingival Folds			
Gingival Mucosa			
Edentulous Ridge/Retromolar area			
Tongue			
Sublingual Area/floor of mouth			
Submandibular area		

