Study Objectives:	
The primary objective of this research is to assess the human factors in relabeling the SaliPen from a prescription-based device to an OTC.
 
Primary performance endpoints:
 
• The user can select the device properly.• The user can use the device as instructed in the IFU.
Study Design:	
This will be a single-center, prospective, open-label study.
 
Screening: Eligible subjects will be included in the study.

Test Participant Recruitment Plan:	
Patients visiting the participating clinic will be asked to participate in the study sequentially (by order of recall or arrival at the clinic).
 
For Phase I, enrollment will be stopped once the goal of eight (8) subjects with xerostomia and eight (8) subjects without xerostomia has been reached.
 
For Phase II, 16 subjects with xerostomia that are evaluated or treated at the clinic will be enrolled sequentially (by order of recall or arrival at the clinic). Patients that have participated in Phase I and have xerostomia will be invited to participate in Phase II, as well.
 
Participants will receive \$25 cash for participating in either phase of this study. Participants in both phases will receive \$50 cash.

	Participants in Phase II will be given the option to keep the SaliPen device they will use in the study.
Inclusion Criteria:	Phase I: Any adult person that is 18 years old or older Phase II: Subjects with xerostomia that are 18 years old or older
Exclusion Criteria:	Phase I: 
• Children and adolescents (persons under 18 years of age)• Persons with experience in the use of SaliPen Phase II: 
• Persons with experience in the use of SaliPen• Children and adolescents (persons under 18 years of age)• Epileptic disorder• Persons that are allergic to the surface materials of the device
◦ Electrodes: coated with gold◦ Body: made of methyl vinyl silicone rubber• Use of a pacemaker• Pregnancy• Psychiatric or psychological disorders• Involuntary muscle movement disorder (such as Parkinson's)• Neurologic disorder in head and neck area
Medical Device Description:	Electrical salivary stimulator system.
Study Endpoints:	Performance Endpoints: 
• Correct selection of the product.• Product use in accordance with the IFU.

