3.2. The study rationale

- Xerostomia (dry mouth) is the subjective feeling of oral dryness. The diagnosis by the practitioner is mostly relying on the patient's feeling.
- Most patients are elderly, many of them with limited mobility.
- Nowadays, those patients are at high risk for COVID-19 infection, morbidity and even mortality.
- The fear of exposure at the practitioner's clinic to obtain an Rx inhibits them from treating their xerostomia with the SaliPen.
- The cost of getting a prescription is an additional burden.
- The SaliPen is an OTC in other parts of the world for years.
- The performance of potential American users of an OTC SaliPen device will be evaluated in this usability study.

As a result, many patients leave their oral dryness untreated, with the well-known consequences of poor oral functions, oral health, daily suffering, and more.

4. Brief Study Description

This Human Factors Validation Testing will assess user interactions to verify the capability of potential users to assess if the study product fits their needs and if they can use it correctly based on the provided Information For User (IFU)?

More specifically, this is a non-comparative case series study and is subdivided into two major parts. Those parts are:

- 1- Phase I: aimed at testing if, based on the IFU, the potential subjects can decide whether the study product is or is not appropriate to treat their condition and,
- 2- Phase II: aimed at assessing whether the users can use the study product correctly without counseling by a health care provider.

Condition or disease	Intervention/treatment
Xerostomia	SaliPen

5. Detailed Study Description

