5.2. Phase II

The study product will be dispensed only to those subjects who will indicate that they volunteerize to participate in this phase of the study.

At Phase II subjects with xerostomia and that are willing to try the study product, will be requested to use it with no training, except for their understanding of the User Manual (internal labeling). Those subjects will use the study product in a supervised clinical setting. Subjects who report any discomfort will be offered the option to pause and remove the device upon such a request.

Correct use verification will be performed by the study investigators. Subjects will answer questions regarding product use, clarity of the IFU, ease of use, etc. Subjects will also receive an exam of their oral cavity.

6. Study Design

Study Type:	Interventional (Clinical Trial)
Enrollment:	Phase I: 16 participants, 8 with xerostomia and 8 without xerostomia
	Phase II: 16 participants with xerostomia (may include participants in Phase I with xerostomia)
Allocation:	N/A
Intervention Model:	Single Group Assignment
Masking:	None (Open Label)
Primary Purpose:	Human Factor Validation - Usability Engineering assessment for OTC labeling
Official Title:	SaliPen Usability Engineering Study for OTC labeling
Study Start Date:	TBD

According to the FDA Guidance document “Applying Human Factors and Usability Engineering to Medical Devices”, a sample of 15 people to detect most of the problems in a user interface constitutes a practical minimum number of participants for human factors validation testing. This sample size theoretically provides the best possibility of detecting user interface design flaws while limiting the amount of resources required.

7. Arms and Interventions

Arm	Intervention/treatment
Experimental: Use of SaliPen medical device	Use according to self-decision.

8. Features to be studied

The points of interaction between the user and the device (User Interface) will be evaluated, including:

- the elements of the device with which the user interacts (i.e., those parts of the device that users see and touch), and
- the IFU (including packaging, labeling, User Manual, etc.).

The following parameters will be studied:

- Hazard: Potential source of harm, if any.
- Use error: User action or lack of action that was different from that expected by the manufacturer.

9. Outcome Measures

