1. Percentage of participants who appropriately will self-select the study product for use under simulated OTC conditions [Phase I]. Following the standard norms for the Rx-to-OTC switch process, this outcome is a validation of potential consumers' ability to self-diagnose the condition and to decide that treatment with the product is appropriate for them.
2. Percentage of participants who correctly will use the study product when dispensed under simulated OTC conditions [Phase II]. Correct use means that the participants will demonstrate the use of the study product according to the guidelines outlined in the User Manual. Following the standard norms for the therapy of Rx-to-OTC switch process, this outcome is a validation of potential consumers' ability to self-treat with the product according to the product's supplied IFU.

10. Eligibility Criteria

Ages Eligible for Study: 18 years of age and older for Phase I and Phase II

Genders Eligible for Study: Female and male

10.1. Inclusion criteria:

- 1- For Phase I: 8 subjects with xerostomia and 8 without that are 18 years old or older
- 2- For Phase II: Subjects with xerostomia that are 18 years old or older

10.2. Exclusion criteria:

- 1- For Phase I:
 - Children and adolescents (persons under 18 years of age)
 - Persons with experience in the use of SaliPen

2- For Phase II: Subjects for whom the study product is not indicated and/or do not agree to participate in Phase II. For the avoidance of doubt, the following conditions are exclusion criteria:

- Persons with experience in the use of SaliPen
- Children and adolescents (persons under 18 years of age)
- Epileptic disorder
- Persons that are allergic to the surface materials of the device
 - Electrodes: coated with gold
 - Body: made of methyl vinyl silicone rubber
- Use of a pacemaker
- Pregnancy
- Psychiatric or psychological disorders
- Involuntary muscle movement disorder (such as Parkinson's)
- Neurologic disorder in head and neck area

11. Reportable Events

An adverse event (AE) is defined as any untoward medical occurrence in a subject during the investigation. Any findings will be documented on the AE CRF.

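### Phase I question 2 does not tell the participant that it asks about the indication only, so a dry-mouth participant who correctly rejects the device can be scored as a failure

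*Combined protocol and SAP*

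**What the plan says.** The aim of Phase I (Section 4) is to test whether, from the labeling, "the potential subjects can decide whether the study product is or is not appropriate to treat their condition". The first outcome (Section 9) covers self-diagnosis and the ability to "decide that treatment with the product is appropriate for them". Section 13 splits this into separate tasks: task 2 is whether the product is indicated for the person, and task 3 is whether the person can use it, cannot use it, or needs medical advice first.

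On the participant's form (Section 15, Phase I) the second question is "2. Does the device fit your needs". The third opens "3. If the device fits your needs, please check a box (only one", and its boxes are: can use, cannot use because of a contraindication, or needs a professional consultation first.

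On the evaluator's sheet (Section 16, Phase I), Step 1 records xerostomia as the indication, separately from contraindications and precautions. Step 3 gives "Total questions/statements for those with dry mouth: 5" and a total of 2 for those without. The pass line is "Passed? (all answers/statements should be correct", matching the 100% rule in Section 13. The Correct answer column has empty Yes/No boxes. No rule says how to fill it or how to score question 3 when it is left blank.

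Section 6 sets "Phase I: 16 participants, 8 with xerostomia and 8 without xerostomia". The synopsis admits "Phase I: Any adult person that is 18 years old or older", and the only Phase I exclusions are minors and people who have used the device before. The study succeeds if 85% of participants pass each phase.

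**The concern.** To a lay reader, whether a device fits one's needs can mean either *I have the problem it treats* or *it is suitable for me*. A person with dry mouth and epilepsy who has understood the warning can sensibly answer No in the second sense. The printed condition then tells that person not to answer question 3, which is the only place where the contraindication could be shown.

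That person has done what Sections 4 and 9 ask, namely decided that the product is not appropriate. The sheet nevertheless scores five items and records a failure. The same marks would come from someone who never realised that the device is for dry mouth. At stake is whether the Phase I percentage can be interpreted in the participants for whom the label warnings matter most.

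**Working it through.** **Plan's item totals.** Question 1 + question 2 + three question 3 statements = 5 for those with dry mouth. Question 1 + question 2 = 2 for those without. Both totals in Section 16 are reproduced.

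**Key implied by the form.** The 5/2 split depends only on whether the person has dry mouth. A dry-mouth participant with epilepsy should therefore be keyed: Q1 Yes, Q2 Yes, can use No, cannot use Yes, needs advice No.

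**Scores under that key, with question 1 answered correctly:**

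| Response | Correct items | Result |
|---|---|---|
| Q2 Yes, then the cannot-use box | 5/5 | pass |
| Q2 No, Q3 skipped, unticked read as No | 3/5 (Q1, can use, needs advice) | fail |
| Q2 No, Q3 skipped, blanks read as failures | 1/5 (Q1) | fail |
| Q2 No, cannot-use box ticked anyway | 4/5 (all but Q2) | fail |

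Every pattern that starts with No at question 2 fails, however blanks are treated. Writing down the implied key would therefore not remove the problem.

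**Who can be affected.** The contraindications on the form are age under 18, epilepsy, and allergy to gold or silicone. Minors are excluded, so epilepsy and the allergies remain, among the 8 participants with xerostomia. The documents give no prevalence and set no quota for such participants.

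**Expected number (assumption: prevalence p = 5%).** 8 × 0.05 = 0.4 people. If half of them answer No at question 2, 0.4 × 0.5 = 0.2 are misrecorded; if all do, 0.4. The chance that at least one such person is enrolled is 1 − 0.95^8 = 0.34.

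**Tolerance.** 0.85 × 16 = 13.6, so 14 passes are needed: 14/16 = 87.5% succeeds and 13/16 = 81.25% does not. Two failures are allowed. One misrecorded participant uses half of that allowance, and three would fail Phase I.

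**Chance of three.** At 5%, the chance of three or more such people among 8 is 1 − (0.6634 + 0.2793 + 0.0515) = 0.0058, about 0.6%. If half answer No (effective rate 2.5%), it is about 0.1%.

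**Effect of one misrecording (assumption: everyone otherwise passes with probability 0.95).** With no affected participant, P(at least 14 of 16 pass) = 0.957. With one participant certain to be failed, at least 14 of the other 15 must pass: 0.95^15 + 15 × 0.05 × 0.95^14 = 0.463 + 0.366 = 0.829. If that participant answers No with probability one half, the figure is (0.957 + 0.829)/2 = 0.893.

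**The case against.** The strongest reply is that the form has one coherent route. Question 3 offers a cannot-use box to people for whom the device fits, which makes sense only if fitting one's needs is compatible with a contraindication. The Step 1 layout, the split between tasks 2 and 3, and the 5/2 totals all point the same way. This stands. A reader might infer that the form offers two equally correct ways to reject the device and that no key could accept both. The documents do not support that as a separate defect: no key for a Yes/No item accepts both answers, and the structure shows which one was meant. What remains is that the participant cannot see this structure and has only the wording of question 2.

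It can also be said that No followed by a skip does not demonstrate task 3, so withholding credit is defensible and the error runs against the product. That is fair as to direction. But the printed condition is what prevents the person from demonstrating task 3, and a failure that does not show which task was missed is of little use in a usability evaluation. The package text is not in the documents, so how often a contraindicated reader would answer No is unknown.

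Finally, a reader might pool the precautions (pacemaker, pregnancy and the others) with the contraindications and assume 20% or 30%, giving 8 × 0.20 = 1.6 or 8 × 0.30 = 2.4 people. The documents give no such rates. For someone told to seek advice first, No at question 2 is also much less clearly a correct answer. Those larger figures should not be used.

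**Conclusion.** The point holds as a wording defect with a small expected effect. Question 2 is meant to test the indication but does not say so, and a contraindicated dry-mouth participant who correctly rejects the device by answering No is scored as a failure, indistinguishable from one who missed the indication. At an assumed 5% prevalence, 0.4 such people are expected among the 8 with xerostomia, and fewer would be misrecorded if only some answer No. One misrecording takes half of the two-failure allowance. Under the stated assumptions it lowers the chance of Phase I success from 0.957 to 0.829.

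A reader might go on to infer that the defect is likely to sink Phase I or that the overall percentage is seriously biased. The documents do not support that: three misrecordings would be needed to fail Phase I on this account alone, and at 5% that is remote. The prevalence, the share answering No and the 0.95 pass probability are assumptions, not figures from the plan. The case for acting is that the error falls on the group the warnings are written for and is almost free to remove.

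**What to change.** - **Question 2:** reword it to ask only about the condition, for example *Do you have the problem this device is meant for?* Key it to the xerostomia row of the Step 1 anamnesis.
- **Question 3:** change the lead-in to *If you answered Yes to question 2*. Every dry-mouth participant who recognises the indication then answers it, and a contraindication is declared there.
- **Participants without dry mouth:** keep the 2-item scoring and do not require question 3. A healthy person without xerostomia would have only the can-use box to tick, which would record a use statement from someone for whom the product is not indicated. This group is half the sample.
- **Answer key:** complete the Correct answer column from the Step 1 anamnesis before seeing the participant's answers, and count unticked question 3 boxes as No.

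Under the revised form, a dry-mouth participant with epilepsy who reads the label correctly answers Yes, ticks the cannot-use box and scores 5/5. A No at question 2 from someone with dry mouth then means that the indication was missed. The cost is two lines of the questionnaire, the matching lines and a scoring note on the evaluation sheet, and IRB approval of the revised form (Section 14.4). No extra participants or visits are needed.

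### The Phase I answer form names the indication and prints the sorted warning conditions, so a pass is only weak evidence that the package label worked

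*Combined protocol and SAP*

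**What the plan says.** Sections 4 and 5.1 give the aim of Phase I: from the labeling on the outside of the package, and with no provider help, subjects decide whether the product suits them. Section 9 makes the percentage who self-select appropriately Outcome 1. Section 13 breaks this into three tasks: knowing the intended use, judging whether the product is indicated for oneself, and judging whether one can use it, cannot, or needs medical advice.

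In the Section 15 questionnaire, subjects read the front and back cover and then answer three closed questions:

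- Question 1: "Is the device for Dry Mouth Relief" (Yes/No).
- Question 2: whether the device fits the subject's needs (Yes/No).
- Question 3: "If the device fits your needs, please check a box (only one". One box is for those who can use the device. A second reads "I cannot use the device because, either" and is followed by three lines (age under 18, epileptic disorder, gold or silicone allergy). A third reads "I need a professional consultation before buying the device because, either" and is followed by five conditions.

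The Section 16 Phase I sheet repeats the lists in Step 2, where the third box reads "I need professional advice before using the device because, either". Its Step 1, numbered before the questionnaire, is a history taken by the evaluator on xerostomia and the same conditions. Step 3 gives "Total questions/statements for those with dry mouth: 5" and "Total questions/statements for those without dry mouth: 2", with the pass rule "Passed? (all answers/statements should be correct".

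**The concern.** A shopper has the package but not this form. If the form carries the indication and the warnings, a correct answer does not show whether the subject got it from the label or from the form.

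Question 1 is the only item for the intended-use task, and it states the intended use. By naming dry mouth it also cues Question 2, where subjects judge whether the product fits them. Question 3 presents the conditions already sorted under the box to tick. The form has no open question, no wrong indication and no distractor condition that would separate label readers from form readers.

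At stake is the reading of Outcome 1 and of one of the two phases that must both succeed under Section 13. The problem has to be solved before enrollment, because a subject who has seen the cues cannot be retested without them.

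**Working it through.** **1. The plan's own figures.** Items scored with dry mouth: Question 1 + Question 2 + three Question 3 statements = 5. Without dry mouth: Question 1 + Question 2 = 2. Both match Step 3. Section 13 requires 85% of participants to pass: 0.85 x 16 = 13.6, so 14 passes are needed (13/16 = 81.25% falls short; 14/16 = 87.5% meets it).

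**2. Route to a pass from the form alone.**

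| Item | Task in Section 13 | Correct answer | What the form gives |
|---|---|---|---|
| Question 1 | Intended use | Yes for 16 of 16 | Names the indication |
| Question 2 | Indicated for oneself | Own xerostomia status | Question 1 has just named dry mouth |
| Question 3 (scored for the 8 with dry mouth) | Can, cannot, or ask first | Own history | 3 + 5 = 8 sorted lines |

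Phase I enrolls adults only, so the under-18 line cannot apply, leaving 8 - 1 = 7 lines. Every scored item can be answered from the form plus self-knowledge.

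**3. Who the Question 3 list can affect.** It can lead a dry-mouth subject with a listed condition to the restrictive box. It can also reassure one with no listed condition, for example a cautious subject with some other illness, that 'can use' is right. Its reach is therefore not confined to subjects with a listed condition.

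**4. How few passes decide the phase.** If two other subjects fail, 14 pass, and one pass that depended on the form separates success from 13/16. If nobody else fails, 16 - 2 = 14 still succeeds and 16 - 3 = 13 does not, so three are needed.

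**5. Illustration in which nobody uses the label (accuracies assumed).** Let a be the chance of Yes on Question 1, and s the chance of being right on each of Questions 2 and 3. The pass probability is a x s x s with dry mouth and a x s without. Adding two binomial counts of 8 gives the chance of at least 14 passes:

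| a | s | Pass, dry mouth | Pass, no dry mouth | Chance of 14 or more |
|---|---|---|---|---|
| 1 | 1 | 1 | 1 | 1.00 |
| 1 | 0.95 | 0.902 | 0.95 | 0.89 |
| 0.95 | 0.95 | 0.857 | 0.902 | 0.70 |
| 0.90 | 0.90 | 0.729 | 0.81 | 0.25 |
| 0.80 | 0.90 | 0.648 | 0.72 | 0.08 |

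Success without use of the label is possible, but only if subjects answer accurately from the form. Blind guessing is not the problem: it passes a subject with probability 1/2 x 1/2 x 1/3 = 1/12 or 1/2 x 1/2 = 1/4, and the chance of 14 or more is about 2 in 10 billion.

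**6. Whether the warnings are tested at all.** The only Phase I enrollment target is 8 with and 8 without xerostomia. If a share p of dry-mouth subjects has a listed condition (p assumed), the chance that none of the 8 does is (1 - p)^8: 66% at p = 5%, 43% at 10%, 17% at 20%, 6% at 30%.

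**The case against.** The strongest reply is that the package is what subjects are told to read, and nothing says it is taken away. If it states dry-mouth relief prominently and lists the same conditions, the form only repeats what is already in hand. The package text is not in the documents, so this cannot be ruled out. It limits what can be said about the size of the effect. It does not restore the missing evidence, since a pass still cannot show which source was used.

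A second reply is that the outcome is self-selection, not label comprehension, and that Question 3 does not print the subject's answer, because the key is the subject's own history. That is correct, and it is why a pass keeps some value: the subject must still match that history to a list. But Sections 4, 5.1 and 13 tie the decision to the label and to knowing the intended use.

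A third reply is that open answers are hard to score. Phase II already uses open questions scored by an evaluator.

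A reader might go further and infer that Phase I passes mean nothing, or that the pass rate is inflated by a known amount. The documents support neither. The accuracies in the illustration are assumed, and without the package text or the case mix no net bias can be stated.

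**Conclusion.** The point holds as a weakness of the instrument that should be fixed before enrollment. The form cues Questions 1 and 2 for all 16 subjects and Question 3 for the 8 in whom it is scored, so a pass is weak evidence that the label worked.

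Confidence is high on the form's wording and on the route to a pass. It is moderate on the consequence, which depends on how much the form adds to an unseen package and on how many subjects have a listed condition. With the threshold at 14 of 16, one to three form-dependent passes could decide the phase; whether any would occur is unknown.

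**What to change.** (a) Make Question 1 open (*What is this device for?*) and score it against a short pre-set key of accepted answers taken from the package.

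(b) Keep the three boxes in Question 3, but remove the condition lists from the subject's questionnaire and from the matching Step 2 text. Keep them only on the evaluator's Step 1 sheet. Score the ticked box against the evaluator's history, and record the subject's stated reason descriptively.

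(c) Take the contraindication and precaution history after the questionnaire is collected. Obtain the xerostomia status needed for the 8/8 quota without drawing attention to dry mouth just before Question 1, for example from clinic records or within a general list of oral symptoms. State any remaining cue as a limitation.

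(d) Report how many of the 8 dry-mouth subjects had a listed condition, and limit the conclusion about the warnings if few did.

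Costs: one short free-text answer is judged under the all-correct rule, so the key must be fixed in advance, and the revised forms need IRB approval (Section 14.4). Visit and staff are unchanged. One limit remains: a dry-mouth subject with no listed condition can still tick 'can use' by default.

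Two minor points can be settled in the same revision but are separate from this one. Scoring Question 3 as a single item changes no pass and affects only the percentage of correct answers, where one wrong tick now still earns 1 of 3 rows (key Yes, No, No against answer No, Yes, No). The third box also differs between the two forms, before buying in Section 15 and before using in Section 16; these must be reconciled.
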